# 4) Allergies and Adverse Drug Reaction

- a) History of allergy to study treatment(s), combination of study treatments or any of its components
- b) History of severe hypersensitivity reaction to any mAb

### 5) Other Exclusion Criteria

a) Prisoners or participants who are involuntarily incarcerated (Note: under certain specific circumstances and only in countries where local regulation permit a person who has been imprisoned may be included or permitted to continue as a participant. Strict conditions apply and BMS approval is required).

b) Participants who are compulsorily detained for treatment of either a psychiatric or physical (eg, infectious disease) illness.

Eligibility criteria for this study have been carefully considered to ensure the safety of the study participants and that the results of the study can be used. It is imperative that participants fully meet all eligibility criteria.

## 6.3 Lifestyle Restrictions

There are no lifestyle restrictions applicable for this study given that the participants will receive the study investigational products (IPs) IV.

### 6.4 Screen Failures

Screen failures are defined as participants who consent to participate in the clinical study but who are not subsequently randomized/entered in the study/included in the analysis population. A minimal set of screen failure information is required to ensure transparent reporting of screen failure participants, to meet the Consolidated Standards of Reporting Trials (CONSORT) publishing requirements, as applicable, and to respond to queries from regulatory authorities. Minimal information includes date of consent, demography, screen failure details, eligibility criteria, and any serious AEs.

## 6.4.1 Retesting During Screening or Lead-In Period

This study permits the re-enrollment of a participant that has discontinued the study as a pretreatment failure (ie, participant has not been randomized/has not been treated). If re-enrolled, the participant must be re-consented.

Retesting of laboratory parameters and/or other assessments within any single Screening or Leadin period will be permitted (in addition to any parameters that require a confirmatory value).

The most current result prior to randomization is the value by which study inclusion will be assessed, as it represents the participant's most current clinical state.

Laboratory parameters and/or assessments that are included in Table 2-2, may be repeated in an effort to find all possible well-qualified participants. Consultation with the Medical Monitor may be needed to identify whether repeat testing of any particular parameter is clinically relevant.

Testing for asymptomatic SARS-CoV-2 infection by RT-PCR or viral antigen is not required. However, some participants may develop suspected or confirmed symptomatic SARS-CoV-2 infection, or be discovered to have asymptomatic SARS-CoV-2 infection during the screening period. In such cases, subjects may be considered eligible for the study after meeting all inclusion/exclusion criteria related to active infection, and after meeting the following criteria:

• At least 10 days (20 days for severe/critical illness) have passed since symptoms first appeared or positive RT-PCR or viral antigen test result, and

- At least 24 hours have passed since last fever without the use of fever-reducing medications,
   and
- Acute symptoms (eg, cough, shortness of breath) have resolved, and
- In the opinion of the investigator, there are no SARS-CoV-2 infection sequelae that may place the participant at a higher risk of receiving investigational treatment.

In the instance of a SARS-CoV-2 infection during screening, the screening period may be extended beyond the protocol-specified timeframe with MM approval.

Any screening tests already performed which could potentially be affected by the SARS-CoV-2 infection or its complications on an individual basis and agreed upon with the MM (eg, safety laboratory tests, SpO2, chest CT scan) should be repeated.

### 7 TREATMENT

### 7.1 Treatments Administered

Study treatment is defined as any investigational treatment(s), marketed product(s), placebo, or medical device intended to be administered to a study participant according to the study randomization or treatment allocation.

Study treatment includes only the Investigational [Medicinal] Product (IP/IMP) and consist of the following:

- BMS-986253
- Nivolumab
- Ipilimumab
- Placebo for BMS-986253 (socium chloride for injection or dextrose for injection)

An IP, also known as IMP in some regions, is defined as a pharmaceutical form of an active substance or placebo being tested or used as a reference in a clinical study, including products already with a marketing authorization but used or assembled (formulated or packaged) differently than the authorized form, or used for an unauthorized indication, or when used to gain further information about the authorized form.

All drugs used in this study qualify as IPs, as per previous text, and their description and storage information are described in Table 7.1-1.

Other medications used as support or escape medication for preventative, diagnostic, or therapeutic reasons, as components of the standard of care for a given diagnosis, are considered as Non-investigational [Medicinal] Product (Non-IP/Non-IMP).

Protocol Amendment No.: 07

Table 7.1-1: Study Treatments for CA027002

Product Description/ Class and Dosage Form	Potency	IP/ Non-IMP	Blinded or Open Label	Packaging/ Appearance	Storage Conditions (per label)	
BMS-986253 Injection		IP	Open label a	Vial	Refer to the label on container and/or pharmacy manual	
BMS-986253 Injection		IP	Open label a	Vial	Refer to the label on container and/or pharmacy manual	
Nivolumab (BMS-936558) solution for injection		IP	Open label a	Vial	Refer to the label on container and/or pharmacy manual	
Ipilimumab solution for injection		IP	Open label a	Vial	Refer to the label on container and/or pharmacy manual	
Ipilimumab solution for injection		IP	Open label a	Vial	Refer to the label on container and/or pharmacy manual	
Normal saline solution for injection b		IP	Open label	Various (local commercial product)	Refer to the label on container	
Dextrose solution for injection b		IP	Open label	Various (local commercial product)	Refer to the label on container	

Abbreviation: IP, Investigational Product.

# 7.2 Handling and Dispensing

The product storage manager should ensure that the study treatment is stored in accordance with the environmental conditions (temperature, light, and humidity) as determined by BMS. If concerns regarding the quality or appearance of the study treatment arise, the study treatment should not be dispensed and BMS should be contacted immediately.

IP documentation must be maintained that includes all processes required to ensure drug is accurately administered. This includes documentation of drug storage, administration and, as applicable, storage temperatures, reconstitution, and use of required processes (eg, required diluents, administration sets).

Protocol Amendment No.: 07

<sup>a The term "open label" refers to the medication as it is upon receipt at the pharmacy. In Part 2 of this trial, BMS-986253/placebo will be prepared, dispensed, and administered in a double-blinded fashion.

<sup>b This will be sourced by the investigative sites if permitted by local regulations.

Infusion-related supplies (eg, IV bags, in-line filters, and sodium chloride solution) will not be supplied by the Sponsor and should be purchased locally if permitted by local regulations.

Placebo in Part 2 must be handled/dispensed/infused in an identical fashion as BMS-986253 in order to maintain the blind.

Please refer to the current version of the IB and/or pharmacy manual for complete storage, handling, dispensing, and infusion information for BMS-986253, placebo, nivolumab, and ipilimumab.

## 7.3 Schedule of Dose for Each Investigational Product

The dosing schedule for each IP is detailed below in Table 7.3-1 and Section 2 for all study parts. For BMS-986253, nivolumab, and ipilimumab, participants may be dosed within a  $\pm$  3-day window. Premedications are not recommended on Cycle 1 Day 1. Additional information can be found in the pharmacy manual.

Protocol Amendment No.: 07

Approved v 8.0

930120018 9.0

Table 7.3-1: Dose, Frequency, Infusion Time, and Sequence of IPs

Cohort	BMS-986253 Dose and Frequency	BMS-986253 Infusion Time (min	Nivolumab Dose and Frequency	Nivolumab Infusion Time (min ■	Ipilimumab Dose and Frequency	Ipilimumab Infusion Time (min)	Order of Drug Administration
			Pa	rt 1			
1A a	2400 mg Q4W		480 mg Q4W	30 min	NA		
1B1 a	2400 mg Q4W		480 mg Q4W	30 min	NA		
1B2 a	1200 mg Q4W		480 mg Q4W	30 min	NA		
1B3 a	$600~\mathrm{mg}~\mathrm{Q4W}$		480 mg Q4W	30 min	NA		
1B4	2400 mg Q2W		480 mg Q4W	30 min	NA		
1B5	1200 mg Q2W		480 mg Q4W	30 min	NA		
1B6	3600 mg Q2W		480 mg Q4W	30 min	NA	_	
1C1	3600 mg Q2W		1 mg/kg Q3W (x 4 doses), followed by 480 mg Q4W	30 min	3 mg/kg Q3W (x 4 doses)		
ici	3000 liig Q2 W			30 IIIII	(x 4 doses)		

Protocol Amendment No.: 07

**Table 7.3-1:** Dose, Frequency, Infusion Time, and Sequence of IPs BMS-986253 BMS-986253 Nivolumab Nivolumab **Ipilimumab Ipilimumab** Order of Drug **Infusion Time Cohort** Dose and **Dose and Infusion Time** Dose and **Infusion Time** Administration (min)h (min)h (min)h Frequency Frequency Frequency Part 2 1 mg/kg Q3Wg 3 mg/kg Q3W (x 4 doses), 2A 3600 mg Q2W followed by (x 4 doses) 480 mg Q4W 1 mg/kg Q3Wg (x 4 doses) 3 mg/kg Q3W Placebo 2B Q2W followed by (x 4 doses) 480 mg Q4W C, Cycle; D, Day; Ipi, ipilimumab; Nivo, nivolumab; QXW, every X weeks. Abbreviations:

Protocol Amendment No.: 07 Date: 17-May-2024

## 7.4 Method of Treatment Assignment and Stratification

During the pre-screening visit, the investigative site will enroll the participant in IRT for assignment of a unique 5-digit participant number designated by BMS. Enrolled participants, including those not dosed, will be assigned sequential participant numbers starting with The participant identifier number (PID) will ultimately be comprised of the site number and participant number. For example, the first participant screened (ie, enrolled) at site number 1, will have a PID of To distinguish Part 1 and Part 2 participants, the first digit of the participant number will always be a 2 for Part 2 participants Once it is determined that the participant meets the eligibility criteria following the screening visit, the investigative site will utilize the IRT to centrally assign the participant into the open dose panel (Part 1) or blinded treatment arm (Part 2). Study treatment will be dispensed at the study visits as listed in Schedule of Activities (Section 2).

#### Part 1

provides a summary of treatment assignment in Part 1. The safety evaluation lead-in (Part 1A) will start with a cohort of participants dosed at 2400 mg of BMS-986253 combined with 480 mg of nivolumab Q4W.

[figure not shown]
After the review of clinical safety assessment of the first 4 participants, the DLT, and the totality of available data, up to

assessment of the first 4 participants, the DLT, and the totality of available data, up to approximately additional participants will be enrolled in the dose-finding phase (Part 1B). Participants will be randomly assigned in an approximately 1:1:1 ratio to Cohorts 1B1, 1B2, and 1B3. Randomization will be performed using an equal randomization with each cohort capped at approximately participants, such that corresponding entries for capped cohort in the randomization list will be skipped.

In the event that the safety lead-in evaluation recommends to evaluate a lower dose of BMS-986253 (1200 mg) prior to start of the randomized dose-finding phase (Part 1B), a cohort of 4 participants will be treated in combination with 480 mg of nivolumab. If there are no safety concerns after the clinical safety assessment, then participants will be randomized in a similar fashion in approximately 1:1 ratio to Cohorts 1B2 and 1B3.

If PK, pharmacodynamic, and/or safety analyses indicate further assessment of a dosing regimen is not warranted and/or assessment of additional dosing regimens is indicated, then randomization will be stopped, and subsequent participants will be assigned sequentially to dosing regimens available at that time. If any dosing regimen evaluates a higher dose of BMS-986253 than previously explored, an initial 4-participant safety lead-in with a 28-day DLT period will be required. Approximately participants will be dosed in the dosing regimen(s) of interest. Additional exploration of a specific dosing regimen may be warranted, in which case a maximum of approximately additional participants will be assigned to a dosing regimen of interest in Part 1B. A maximum of approximately participants will be dosed in Part 1B.

Part 1C is a safety evaluation of BMS-986253 in combination with nivolumab and ipilimumab. Part 1C will begin once the DLT period is completed for Cohort 1B6 (BMS-986253 3600 mg Q2W + nivolumab 480 mg Q4W), and will enroll simultaneously with Part 1B. In Part 1C, participants

Protocol Amendment No.: 07 Date: 17-May-2024

Protocol Amendment No.: 07

#### Part 2

Part 2 will begin after determination of the RP2D from Part 1 and generating safety data on the triplet combination of BMS-986253 plus nivolumab plus ipilimumab in Part 1C. Part 2 is a double-blind randomized evaluation of BMS-986253 plus nivolumab plus ipilimumab versus placebo plus nivolumab plus ipilimumab and will be conducted to evaluate the efficacy of BMS-986253 in participants who are refractory to anti-PD-(L)1 therapy.

IRT will be used to track the enrollment number.

Once assigned a subject ID in IRT, participants that have met all eligibility criteria will be randomized through IRT (up to 3 days prior to C1D1). The following information is required prior to participant randomization:

- Participant subject ID
- Date of birth
- Gender
- Screening serum IL-8 level

• Screening LDH

Participants will be randomized in a 1:1 ratio to treatment and control arms. Three stratification factors will be used during randomization: screening

and screening LDH (≤ ULN or > ULN). Screening serum IL-8 data will be transferred directly from the analyzing laboratory to IRT. BRAF status and screening LDH must be entered in eCRF by the site.

Approximately participants will be randomized in Part 2.

The exact procedures for using the IRT will be detailed in the IRT manual.

#### 7.5 Blinding

#### 7.5.1 Part 1

Part 1 of this study is open label, with randomized and non-randomized portions. Data emerging from this portion of the study may be necessary to inform timely decisions for adjusting procedures in subsequent portions of the study, including early termination of the study, requiring access to IRT treatment codes in either the randomized or non-randomized portions of the study. Additionally, treatment assignments may facilitate optimization of the bioanalytical analysis of samples.

Designated members of the study team, as well as the Bioanalytical and/or clinical pharmacology groups of the Sponsor can access IRT treatment codes prior to the formal locking of the study database *for these purposes*. This access to the treatment codes will not impact the data integrity of the study.

#### 7.5.2 Part 2

Part 2 of the study will be conducted as a double-blind study. The Sponsor, participants, investigator, and site staff will be blinded to the study therapy administered. Each investigative site must assign an unblinded pharmacist/designee, and an unblinded site monitor will be assigned by Sponsor to provide oversight of drug supply and other unblinded study documentation.

Before breaking the blind of an individual participant's treatment, the investigator should determine that the unblinded information is necessary (ie, that it will alter the participant's immediate management). In many cases, particularly when the emergency is clearly not related to the investigational product, the problem may be properly managed by assuming that the participant is receiving active product. It is highly desirable that the decision to unblind treatment assignment be discussed with the Medical Monitor, but the investigator always has ultimate authority for the decision to unblind. The actual TASK of unblinding can be delegated by the investigator to a designee assigned the task on the Delegation of Authority. The principal investigator or appointed designee should only call in for emergency unblinding AFTER the decision to unblind the participant has been documented.

For this study, the method of unblinding for emergency purposes is via the IRT system. For information on how to unblind in an emergency, consult the IRT manual.

In cases of accidental unblinding, contact the BMS Study Director/Medical Monitor (or designee) and ensure every attempt is made to preserve the blind.

Any request to unblind a participant for non-emergency purposes should be discussed with the BMS Study Director/Medical Monitor (or designee).

In case of an emergency, the investigator(s) has unrestricted access to randomization information via the IRT and is capable of breaking the blind through the IRT system without prior approval from Sponsor. Following the unblinding, the investigator shall notify the Medical Monitor and/or study director.

Designated staff of Bristol-Myers Squibb Company may be unblinded prior to database lock to facilitate the bioanalytical analysis of pharmacokinetic samples and immunogenicity. Bioanalytical scientists in the Bioanalytical Sciences department of Bristol-Myers Squibb Company (or a designee in the external central bioanalytical laboratory) may be unblinded to (may obtain) the randomized treatment assignments in order to minimize unnecessary bioanalytical analysis of samples.

If a participant is assessed by the investigator to have disease progression, and unblinding is considered necessary to inform the appropriate subsequent anti-cancer therapy, the study treatment assignment for the participant can be obtained by the investigator through IRT for non-emergency unblinding. The investigator should follow the procedures outlined in the IRT manual to obtain the participant's study treatment assignment. The BMS central study team (including but not limited to clinical, statistics, data management) will remain blinded to treatment assignment.

The study will remain blinded until the database lock for as as described in the statistical analysis plan. If an interim analysis is conducted, the Sponsor may be unblinded

Protocol Amendment No.: 07

to the results after accrual to the study has completed and if the primary endpoint is met (as per Section 10).

Once the database lock for the final analysis is completed, the Sponsor and Investigators will be unblinded to treatment assignments; participants on the control arm will no longer receive placebo and will no longer have study visits on Day 15 of each cycle. Similarly, if BMS-986253 is discontinued for any participants (in accordance with Sections 7.6.1, 7.6.4, or 8.1), they will no longer have study visits on Day 15 of each cycle.

## 7.6 Dosage Modification

## 7.6.1 Dose-limiting Toxicities

DLTs will be defined based on the incidence, intensity, and duration of AEs that are possibly related to study treatment. The DLT period will be 4 weeks (28 days). Any toxicities that occur beyond the DLT period will be accounted for in making final dose level decisions.

Participants that experience a DLT or are discontinued due to a DLT in the 4-week combination treatment DLT period, will be considered as DLT-evaluable participants for the safety evaluation period. Participants who withdraw from the study during the DLT evaluation period, for reasons other than a DLT, will not be considered as DLT-evaluable participants and may be replaced with a new participant at the same dose level. All participants who receive treatment will be included in the evaluation, regardless of whether they are DLT evaluable or not.

[figure not shown]
The incidence of DLT(s) during the 4-week DLT evaluation period will be used in the dose decisions for rest of the study, including in the dose-finding phase to define the RP2D or MTD. AEs occurring after the DLT period will be considered for the purposes of defining the RP2D upon agreement between the Sponsor, Medical Monitor, and investigators.

Participants experiencing a DLT will not be re-treated with study treatment, and will enter the safety follow-up period of the study, unless the investigator determines that one of the agents must be discontinued due to a DLT attributed to that agent alone.

AEs will be graded according to the NCI CTCAE v4.03.

Protocol Amendment No.: 07

Protocol Amendment No.: 07

# 7.6.2 Management Algorithms for Immuno-oncology Agents

I-O agents are associated with irAEs that can differ in severity and duration from AEs caused by other therapeutic classes. BMS-986253, nivolumab, and ipilimumab are considered I-O agents in this protocol. Early recognition and management of irAEs associated with I-O agents may mitigate severe toxicity. Management algorithms have been developed from extensive experience with nivolumab to assist investigators in assessing and managing the following groups of irAEs:

- Gastrointestinal
- Renal
- Pulmonary
- Hepatic
- Endocrinopathies

Protocol Amendment No.: 07

- Skin
- Neurological
- Myocarditis

The clinical nature of AEs noted with BMS-986253 will determine the role of the algorithms for use in toxicities related to its use in this study. The algorithms recommended for the management of irAEs in this protocol are in Appendix 6.

## 7.6.3 Dose Delays Due to Toxicity

Dose delay criteria apply for all drug-related AEs, regardless of whether the event is attributed to BMS-986253 (or placebo), nivolumab, or ipilimumab. Delay administration of all study drugs if any of the delay criteria listed below are met.

- Potential DLTs, until DLT relatedness is defined.
- Select AEs and laboratory abnormalities:
  - $\geq$  Grade 2 pneumonitis.
  - ≥ Grade 2 abnormality in AST, ALT, or total bilirubin.
  - $\geq$  Grade 2 creatinine.
  - $\geq$  Grade 2 diarrhea or colitis.
  - $\geq$  Grade 2 neurological AE.
  - AE, laboratory abnormality, or concurrent illness that, in the judgment of the investigator, warrants delaying study treatment administration.
- Confirmed SARS-CoV-2 infection.

For participants who require delay, re-evaluate weekly, or more frequently, if clinically indicated and resume dosing when criteria to resume treatment are met (see Section 7.6.4). Continue tumor assessments per protocol even if dosing is delayed.

Criteria for participants who are required to permanently discontinue study treatments is listed in Section 8.1. Participants not meeting guidelines for permanent discontinuation will be permitted to resume therapy based on the criteria specified below in Section 7.6.4. Participants eligible to resume study therapy will resume study therapy at the nominal treatment visit following their last received study medication dose.

The end of cycle tumor assessments, such as CT, MRI, or positive emission tomography (PET), will continue on an every 8 weeks (Q8W) schedule relative to the participant's first dose, regardless of any treatment delay incurred.

# 7.6.3.1 Criteria for Dose Delay Secondary to Changes in AST or ALT for Participants with HCC

Participants with HCC who experience the following must have the study drug delayed:

- If a participant has a baseline AST or ALT that is within normal limits, delay dosing for drug-related > Grade 2 toxicity (2 grade shift). If a participant has baseline AST or ALT within the Grade 1 toxicity range, delay dosing for drug-related > Grade 3 toxicity (2 grade shift)
- If a participant has baseline AST or ALT within the Grade 2 toxicity range, delay dosing for a 2-fold drug-related increase in AST or ALT or for AST or ALT values 8× ULN (whichever is lower)
- It is recommended to monitor elevations in AST or ALT approximately every 3 days until levels peak and begin to decline. Dosing of study drugs can be resumed where criteria to resume treatment are met (Section 7.6.4).

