# 7.6.3.2 Protocol-Specific Recommendation for Management of Hepatic Events in HCC Participants

The algorithms recommended for the management of irAEs in this protocol are in Appendix 6. Protocol-specific recommendation for the management of hepatic events in HCC participants are as follows:

- Dose delay criteria for hepatic events are outlined in Section 7.6.3.1. If AST or ALT levels do not improve with a dose delay of 3 to 5 days, or if the levels worsen, steroid therapy should be initiated at 0.5 mg/kg/day to 2 mg/kg/day methylprednisolone or oral equivalent
- For ALT or AST levels > 8× ULN, steroid therapy should be initiated promptly at 1 mg/kg/day to 2 mg/kg/day methylprednisolone IV, intramuscularly, or oral equivalent
- For all participants receiving steroid treatment for hepatic events, the BMS Medical Monitor should be consulted within 24 hours after initiation of steroids. Gastroenterology consult is recommended
- If AST or ALT levels do not improve within 3 to 5 days after the start of steroid therapy, or the levels worsen after the start of steroid therapy, discussion with the BMS Medical Monitor regarding the possibility of adding mycophenolate mofetil 1 g twice daily should occur
- Tapering of steroids can start once AST or ALT levels have declined by 1 CTCAE grade. Steroids should be tapered slowly, over no less than 1 month
- As outlined in Section 7.6.4, study therapy may resume when AST or ALT have returned to Grade 1 or baseline unless the AE meets the criteria for permanent discontinuation (Section 8.2). The BMS Medical Monitor must be consulted prior to resuming study treatment for all participants who required steroid intervention.

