#### • Criteria for HCC Participants:

- Participants with baseline Grade 1 AST, ALT, or total bilirubin who require dose delays, for reasons other than a drug-related hepatic event, may resume treatment in the presence of Grade 2 AST, ALT, or total bilirubin increases.
- Participants who require dose delays for drug-related increased AST, ALT, or bilirubin may resume treatment when hepatic parameters are at baseline or Grade 1, and after discussion with the BMS Medical Monitor
- Participants with AST, ALT or bilirubin values meeting permanent discontinuation parameters (Section 7.6.1) should have treatment permanently discontinued.

• Drug-related pulmonary toxicity, diarrhea, or colitis, must have resolved to baseline before treatment is resumed. Participants with persistent Grade 1 pneumonitis after completion of a steroid taper over at least 1 month, may be eligible for re-treatment if discussed with, and approved by, the BMS Medical Monitor.

- Participants with drug-related endocrinopathies adequately controlled with only physiologic hormone replacement may resume treatment.
- Participants with confirmed SARS-CoV-2 infection may resume treatment after 1) at least 10 days (20 days for severe/critical illness) have passed since symptoms first appeared, positive RT-PCR test result, or positive viral antigen test result, 2) resolution of acute symptoms (including at least 24 hours has passed since last fever without fever reducing medications), 3) evaluation by the investigator with confirmation that there are no sequelae that would place the participant at a higher risk of receiving investigational treatment, and 4) consultation by the Medical Monitor. For suspected cases, treatment may also resume if SARS-CoV-2 infection is ruled-out and other criteria to resume treatment are met.
  - Prior to re-initiating on-study treatment in a participant with a dosing delay lasting
     ≥ 8 weeks due to SARS-CoV-2 infection, the Medical Monitor/designee must be
     consulted.

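### Section 7.6.3.1 (HCC, Part 1C only): the printed AST/ALT dose-delay thresholds first trigger at a 3-grade shift but are labelled a 2-grade shift (sign to be confirmed in the source PDF)

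*Combined protocol and SAP*

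**What the plan says.** Section 7.6.3.1 is limited by its heading to AST or ALT changes in HCC participants, and Section 6.1 admits HCC to Part 1C only. The section says that dosing must be delayed, with a trigger that depends on the baseline value:

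- Normal baseline: "delay dosing for drug-related > Grade 2 toxicity (2 grade shift").
- Grade 1 baseline: "delay dosing for drug-related > Grade 3 toxicity (2 grade shift").
- Grade 2 baseline: no grade is named. The trigger is a doubling that is drug-related, "or for AST or ALT values 8× ULN (whichever is lower").

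The parent Section 7.6.3 covers all tumor types. It opens with "Delay administration of all study drugs if any of the delay criteria listed below are met", and its list includes "≥ Grade 2 abnormality in AST, ALT, or total bilirubin". It does not mention HCC. Section 7.6.3.2, which is for HCC only, states: "Dose delay criteria for hepatic events are outlined in Section 7.6.3.1". In Section 7.6.4 the HCC resume rule reads "Participants who require dose delays for drug-related increased AST, ALT, or bilirubin may resume treatment" once the liver values are back at baseline or Grade 1 and the medical monitor has been consulted.

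**The concern.** In each of the first two clauses the threshold and the bracketed label beside it are meant to say the same thing, and as printed they do not. A site that follows the sign keeps dosing a participant who has gone from normal to Grade 2, or from Grade 1 to Grade 3. A site that follows the label stops. Both can claim to be following the protocol.

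The rule is a mandatory liver-toxicity hold on a regimen that includes nivolumab and ipilimumab. The cost of the looser reading is one further grade of drug-related AST/ALT elevation before the hold. A smaller cost is that delays recorded in HCC participants may not mean the same thing at every site.

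**Working it through.** **Inputs.** The two triggers and their common label are from Section 7.6.3.1. Grades are whole numbers, and normal is counted as Grade 0.

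**Formula.** Shift at first trigger = lowest grade that meets the condition − baseline grade. The plan's own figure, from the label, is 2 at both baselines.

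| Baseline | Sign | First grade that triggers | Shift | Label |
|---|---|---|---|---|
| Normal (0) | > Grade 2, as printed | 3 | 3 − 0 = 3 | 2 |
| Grade 1 | > Grade 3, as printed | 4 | 4 − 1 = 3 | 2 |
| Normal (0) | ≥ Grade 2 | 2 | 2 − 0 = 2 | 2 |
| Grade 1 | ≥ Grade 3 | 3 | 3 − 1 = 2 | 2 |

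The strict sign does not reproduce the label; the discrepancy is 3 − 2 = 1 grade in both clauses. The inclusive sign reproduces it in both.

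**Does other text settle the sign?** No. The HCC resume rule in 7.6.4 asks for a return to baseline or Grade 1, which fits either sign. With ≥, the normal-baseline trigger coincides with the general Grade 2 trigger in 7.6.3. That is tidy but not proof, since an HCC rule could be more permissive by design. The label is the only direct evidence for ≥.

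**Could the sign be an extraction fault?** Possibly.

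- In favour: Section 2 of Appendix 8 prints the 10 to 15 mm node range with two ≤ signs, while Section 3 of that appendix gives it as ≥ 10 to < 15 mm. The 8× ULN limit in 7.6.3.1 has no sign at all.
- Against: ≥ is printed correctly in 7.6.3 immediately above, in the encephalopathy exclusion in 6.2, and in the 8-week rule for SARS-CoV-2 delays in 7.6.4.
- Neutral: an odd Grade > 1 in the HCC inclusion criteria recurs in the Appendix 13 change history for Revised Protocol 02. It may be what the authors typed, so it says little about extraction.

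**Where 7.6.3 and 7.6.3.1 differ whichever sign is right.** The general bullet would hold a Grade 1-baseline participant at Grade 2, and 7.6.3.1 would not. For a Grade 2 baseline of b × ULN, 7.6.3.1 triggers at min(2b, 8) × ULN. For b = 3, 4 and 5 this is min(6, 8) = 6, min(8, 8) = 8 and min(10, 8) = 8. At the HCC entry cap of 5× ULN (Section 6.1) that is 8/5 = 1.6-fold. The documents give no CTCAE grade limits, so b = 3 to 5 is an illustrative range. These figures show how much more permissive the HCC rule is. They do not measure an error.

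**The case against.** The strongest reply is that the point rests on one character in machine-read text, in a document where at least one other inequality is visibly garbled. If the source prints ≥, nothing is wrong. If it prints >, the label shows what was meant. The first part stands as a condition: the source must be checked before anything is changed. It does not dispose of the point, because ≥ survives close by and a fault in extraction is possible but not shown. The second part is an argument for making the correction, since a mandatory threshold should not need its label to correct it.

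It is also fair that other safeguards exist. Section 7.6.3 lets the investigator delay on judgment, and 7.6.3.2 calls for prompt steroids above 8× ULN. Potential dose-limiting toxicities are themselves a delay trigger. Section 7.6.4 sends HCC participants with "AST, ALT or bilirubin values meeting permanent discontinuation parameters (Section 7.6.1") to criteria that are redacted, and these may already govern high grades.

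A reader might go further and infer that 7.6.3 and 7.6.3.1 contradict each other, so that HCC participants are bound by two AST/ALT rules, or that HCC bilirubin is left without a delay rule. The documents do not support this:

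- 7.6.3.1 is a subsection of 7.6.3 written for HCC alone, and 7.6.3.2 sends HCC hepatic delay criteria to it.
- If the general bullet also bound for AST/ALT, the Grade 1 and Grade 2 baseline clauses would never decide anything.
- The protocol uses the same pattern, a general rule followed by an HCC rule with no word of exception, for hepatic eligibility (6.1) and for potential drug-induced liver injury (9.2.8).
- The heading of 7.6.3.1 is confined to AST or ALT, so bilirubin naturally stays under 7.6.3.

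What is left is a cross-reference that would help sites.

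**Conclusion.** The point holds for the text as printed. Both grade thresholds in 7.6.3.1 contradict their own label by one grade, in the direction of a later hold. Severity is minor.

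The conclusion assumes that the printed > is in the source and that the label, not the sign, expresses the intent. A reader might take this as a confirmed sign error in the protocol, or as evidence that participants were dosed unsafely. Neither follows: the source sign is unverified, and nothing in the documents shows how sites applied the rule.

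The reach is narrow. Only HCC participants in Part 1C are affected, and the number still on treatment is not stated. Section 5.5.2 reports that the recommended Phase 2 dose has already been selected. Part 2 enrols melanoma only, so its ORR analysis is untouched. No participant count or clinical frequency is claimed.

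**What to change.** Check the two signs in the source PDF. If > is there, change 7.6.3.1 to ≥ Grade 2 for a normal baseline and ≥ Grade 3 for a Grade 1 baseline, and keep the label. If the source already has ≥, no correction is needed.

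Optionally, and as a clarification only, add to the AST/ALT/bilirubin bullet in 7.6.3 that AST and ALT in HCC participants follow Section 7.6.3.1, with bilirubin remaining under 7.6.3.

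The cost is two characters and at most one clause, in an amendment or administrative letter. Data collection and analysis do not change.
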